Of 445 participants who were classified as either having no evidence of liver disease (n = 335) or nonspecific changes (n= 110) in 2007, 28 (6.29%) participants developed CFLD with portal hypertension by 2017. This comprised 15/110 (13.63%) participants who had NSCFLD and 13/335 (3.88%) participants who has NoLD at baseline in 2007 (risk difference 9.76% 95%C1 3.02-16.49 P<.001). The incidence of CFLD with portal hypertension was 7.51 per 1000 person years of follow-up (95% CI 4.99-10.86). The incidence rate for participants under 10 years of age in 2007 was 10.77 per 1000 person years of follow-up (95% CI 6.97-15.9) compared to 2.13 (95%CI 0.42-6.23) in participants over 10 years of age, incidence rate difference 8.63 (95% CI 3.77-13.55 P<.05). No participant older than 10 years of age in 2007 who was classified as NoLD progressed to CFLD by 2017 (median age at follow-up 22.86 years IQR 5.2). Among 355 participants with NoLD in 2007 13 (3.88%) progressed to CFLD with PH, while 35.5% (119/335) displayed nonspecific evidence of liver disease at follow-up in 2017.

By 2017 18/35 (51.43%) participants with CFLD had died compared to 21/110 (19.09%) with NSCFLD and 32/335 (9.55%) with NoLD (P<.001) Using patient years of follow-up as the denominator, the mortality rate for participants with CFLD was 7.75 (95%CI 4.59-12.25) per 100 person years of follow-up (PYRS), for those with NSCFLD 2.34/100PYRS (95%CI 1.48 – 3.57) and 1.13 /100PYRS (95%CI 0.77-1.59) for those with NoLD. The mortality rate difference between those with CFLD and the combined group of NoLD and NSCFLD was 6.33 (95%CI 2.73-9.3) per 100 PYRS (P<.05). Four participants who developed CFLD during follow-up died, two of whom were under 15 years of age. The median age at death of participants without liver disease was 13.25 (IQR 6.33) years while the median age of death of the 49 participants without liver disease was 13.25 (IQR 5.0) p = NS. Of those with CFLD who died during follow-up 9/18(50%) died from hepatic causes of whom

P.I. [name] 4/8 received a liver transplant while 8/18 (44.4%) died from pulmonary causes. By combining the liver-specific focus of the ILSCFLD with ENHANCE the power to elucidate the effects of the CFTR modulators on CFLD is greatly enhanced.

Clinical trials of CFTR modulators have specifically excluded people with CFLD, so we know very little about the effects of modulators in this group. **RECOVER will include a large number of children, adolescents and adults with CFLD (with a longitudinal dataset) in whom we will be able to test the hypothesis that CFTR modulation improves indices of CFLD.**

LCI/CT

CFORMS examined the real-world clinical impact of LUM/IVA in Irish children using LCI and spirometrycontrolled CT scores as outcome measures. We built the study on strong relationships between the clinical sites the ECFS CTN centers for MBW ([name]) and CT imaging ([name], LungAnalysis) to ensure accurate measurement of meaningful outcomes. CFORMS collected LCI data at 4 Irish Centers and CT data at one center in collaboration with the CF Registry of Ireland (CFRI). We recruited a group of controls from the Royal Brompton Hospital, UK, where, at the outset of the study LUM/IVA was not reimbursed for children aged 6-11 homozygous for the F508del mutation. We found no statistically significant change from baseline in LCI among cases, and no difference in rates of change between cases and controls. This was also the case for FEV1 (Table 1). These data are being prepared for publication.

Change from baseline	age from baseline Cases				Controls	
	n	Mean (95%Cl)	p-value	n	Mean (95%Cl)	p-value
LCI _{2.5}	51	-0.34 (-0.95 to 0.26)	p=0.26	13	-0.71 (-2.1 to 0.68)	p=0.31
ppFEV ₁	71	-2.45 (-4.44 to 2.54)	p=0.66	14	5.51 (-1.76 to 12.78)	p=0.14

Table 1. Change from baseline in LCI in a cohort of children homozygous for the F508del mutation, aged 6-11 on treatment with Lumacaftor/Ivacaftor (Cases) and on no treatment (controls).

We carried out spirometry-controlled CT scans at baseline, one year and two years after the introduction of LUM/IVA in 35 children aged 6-11, homozygous for the F508del mutation. Standardization of the scanner output, protocol and data transfer was managed through the LungAnalysis team. Images were scored using the Perth Rotterdam Annotated Grid Morphometric Analysis (PRAGMA) scoring system. Over the course of 2 years on LUM/IVA, while improvements were seen in the mean air trapping scores, bronchiectasis scores increased (Table 2). These data suggest that LUM/IVA can improve air trapping but does not prevent the progression of bronchiectasis in these young children with CF. The data were presented at NACFC 2021 and currently being submitted for publication. Ongoing work is examining the airway wall and artery dimensions in detail in these sans using specifically developed proprietary software in an automated fashion.

PRAGMA Score	E	Baseline		Year 1			
	Mean (95% CI) n=32		Mean (95% CI) n=32	Mean (p-value	
% Bronchiectasis	0.82	(0.48 - 1.16)	0.85	(0.51 - 1.19)	1.24	(0.89 - 1.60)	0.005
% Disease	2.78	(2.12 - 3.45)	2.46	(1.79 - 3.14)	2.25	(1.55 - 2.94)	0.138
% Trapped Air	0.13	(0.09 – 0.16)	0.10	(0.07 – 0.14)	0.07	(0.03 – 0.11)	0.016
% Mucous plugging	0.57	(0.31 – 0.83)	0.28	(0.01 - 0.54)	0.33	(0.04 - 0.62)	0.221

Table 2. Change from baseline in PRAGMA CT scores in 35 children homozygous for the F508del mutation, aged 6-11 on treatment with Lumacaftor/Ivacaftor.

PRELIMINARY data from RECOVER Parent Study

Despite unexpectedly accelerated approval of ETI in Europe in 2020 and a global pandemic, we have reasonable levels of recruitment to date (85% target) and retention of subjects in the first phase (12+) of RECOVER. One-year outcomes were presented at ECFS 2022 (Table 3 below) and Phase 2 of RECOVER (6-11) is continuing to recruit subjects. Figure 4 below shows significant differences in baseline (pretreatment) values for FEV1 and LCI in the 12+ and 6-11 groups, underlining the 'normalization' of LCI in younger children

P.I. [name]

and highlighting the need for more sensitive outcome measures in this group. Baseline (n=78) and 1 year (n=65) spirometry-controlled CT scans have been analysed and will be presented at ECFS and published shortly. Table 4 below summarises the PRAGMA scores analysed to date (unpublished). Table 3 outlines the key available data currently from the first phase of RECOVER showing significant improvements in all measured indices over 6 and 12 months. Over 6 months of ETI use, global CF Abd scores improved significantly from 15.0 \pm 1.4 to 10.7 \pm 1.1; p<0.0001, with significant improvements in sub-scores for domains of 'pain', 'GERD', 'impairment of quality of life' and 'appetite' but not 'disorders of bowel movement'.

	В	aseline (N	=114)		6 m (N=1	03) 12 m (N=90)		BL v all FU	BL v 6m	6m v 12m		
	N	Mean	Std Dev	N	Mean	Std Dev	N	Mean	Std Dev	p-value	p-value	p-value
Sweat Chloride	107	85.78	18.054	94	44.92	18.886	80	44.23	18.936	<.0001	<.0001	0.7358
LCI	82	12.21	3.829	83	10.14	3.689	49	9.85	4.274	<.0001	<.0001	0.3187
pp FEV1	114	83.65	15.399	82	91.73	16.032	87	92.11	16.319	<.0001	<.0001	0.7356
Weight z score	114	0.07	0.812	103	0.32	0.790	90	0.27	0.827	<.0001	<.0001	0.1253
BMI z score	114	0.12	0.819	103	0.36	0.792	90	0.28	0.863	<.0001	<.0001	0.0484
FeNO	112	13.59	10.407	103	16.30	12.397	90	15.96	12.397	0.0118	0.0192	0.7827
CFQR-RD	37	83.32	15.212	27	97.20	7.508	22	95.49	8.792	<.0001	<.0001	0.4386

 Table 3. Available cleaned data from people with CF aged 12 and over and one or more copies of

 F508del from the RECOVER study.

	All Participants						
	Baseline (N=85)			12 months (N=64)			Baseline v 12 mths
Variable	Ν	Mean	Std Error	Ν	Mean	Std Error	p-value
% Bronchiectasis	85	3.86	0.428	64	3.29	0.388	0.3256
% Disease	85	7.34	0.697	64	3.98	0.406	0.0001
% Trapped Air	85	20.61	1.606	63	11.48	1.749	0.0002
% Mucous plugging	85	2.22	0.351	64	0.11	0.042	<.0001
% Bronchial Wall Thickening	85	1.21	0.114	64	0.55	0.070	<.0001
	F508del/F508del						
	Baseline (N=55)			12 months (N=41)			Baseline v 12 mths
Variable	N	Mean	Std Error	N	Mean	Std Error	p-value
% Bronchiectasis	55	3.27	0.449	41	2.49	0.365	0.1769
% Disease	55	5.64	0.738	41	3.09	0.396	0.0030
% Trapped Air	55	13.90	1.790	41	9.01	1.666	0.0485
% Mucous plugging	55	1.35	0.335	41	0.07	0.033	0.0003
% Bronchial Wall Thickening	55	0.98	0.110	41	0.52	0.080	0.0010
	F508del/Minimum function						
	Baseline (N=30)			12 months (N=23)			Baseline v 12 mths

	(N=30)			(N=23)			v 12 mths
Variable	Ν	Mean	Std Error	Ν	Mean	Std Error	p-value
% Bronchiectasis	30	4.44	0.819	23	4.09	0.809	0.7605
% Disease	30	9.03	1.317	23	4.86	0.825	0.0098
% Trapped Air	30	27.33	2.856	22	13.96	3.644	0.0057
% Mucous plugging	30	3.08	0.727	23	0.16	0.098	0.0002
% Bronchial Wall Thickening	30	1.43	0.235	23	0.58	0.121	0.0022

Table 4. PRAGMA CF scores from the RECOVER study demonstrating no change to bronchiectasis scores but substantial improvements in overall disease, trapped air, mucus plugging and bronchial wall thickening with ETI.

[figure not shown]

Figure 4. Baseline (pre-treatment) FEV1 and LCI in 12+ and 6-11 cohorts in the RECOVER study.

Study Team and Collaborators Strengths

RECOVERwill utilize our existing collaborative clinical research experience, and develop collaborations with leading international experts to ensure we can deliver on the great potential that exists. We have worked collaboratively with the Guy's and St Thomas' NHS Foundation Trust on a previous multi-centre investigator led study(124) in addition to CFORMS. The adult CF centres at St Vincent's University Hospital and Belfast City Hospital have considerable experience in CF clinical trials and investigator led studies and are both part of the ECFS clinical trial network. **Our collective experience with clinical trials and collaborative investigator led studies puts us in a strong position** to deliver on this multi-centre real-world project.

We have brought together a team of collaborators who are leading experts in their individual areas and will bring experience along with their expertise in terms of helping us to ensure the study achieves its aims.

Optimising the Research Potential from RECOVER

The design of RECOVER is specifically aimed at maximizing the research benefit (and ultimately the benefit to people with CF) from this cohort of children, adolescents and adults with CF. Our aim with this study is collect as comprehensive as possible an array of biological samples and clinical data from this cohort, and to follow them longitudinally. After the end of RECOVER, we envisage an ongoing surveillance study involving this group, in collaboration with our registry partners so that we can continue to learn about the longer-term impacts of these treatments. In addition, our sample storage plan associated with RECOVER will allow us to work with collaborators and collect, aliquot and store biological samples that will magnify the benefit of the study in light of the fact that these samples will be linked to a well phenotyped cohort with a wide array of useful clinical outcome measures.

EXPERIMENTAL DESIGN AND METHODS

Study Design

RECOVER is a multi-centre, cohort study which takes part in seven paediatric and adult sites across Ireland and the UK over a two-year period (parent study) and a further five years follow up (extension study) in conjunction with the CF Registry of Ireland (CFRI) and the UK CF registry. On the basis that drug will become available first for people aged 12 and over, the first phase, RECOVER12+ will recruit children 12 years and older and adults. This will be followed by the second phase, RECOVER6, recruiting children aged 6-11 years who will likely be starting on drug approximately a year after the older cohort. Data collection for each of these phases will occur over a two year period (Parent Study), and will overlap by 1-2 years. Subsequent to the twoyear period, participants will enter an extension study for a period of five years, with a scaled back programme of assessments occurring annually or biennially. For subjects in both these cohorts, the decision to implement Kaftrio treatment is made completely independently of the decision to enter the study. The investigators will

follow the requirements of the local approved Kaftrio SmPC for the patient management as detailed in the 'special warnings and precautions for use' (e.g. management of hepatic impairment, rash, ophthalmological monitoring, between others), and for the management of interaction with other medicinal products and other forms of interactions.

The 6-11 year cohort will only be enrolled when the license is extended to this age group, and treatment with Kaftrio will only occur in the context of prescription by a physician in compliance with marketing authorisation and the SPC.

The study will have its base in RCSI and Children's Health Ireland (Crumlin) in Dublin, where the PI and project manager will be based and will co-ordinate all aspects of study conduct, training and management. The co-Lead PI, [name] is based at Imperial College and Guy's and St Thomas' NHS Foundation Trust. The statistical, data management and bioinformatics aspects of the study will be coordinated through CFRI for the parent study and CHI for the extension study. Guy's and St Thomas' NHS Foundation Trustwill be the central LCI training and over-reading site. All sites will have their CT scanning protocols for the study optimized and standardized through the Lung Analysis core at the Erasmus Medical Centre in Rotterdam.

List of Parties

Name	Role	Primary Affiliation	Secondary Affiliation		
Core Study Team for	Parent Study				
[name]	Lead PI	RCSI, Dublin	Children's Health Ireland, Dublin		
[name]	Co-PI	Imperial College, London	Guy's and St Thomas' NHS		
			Foundation Trust London		
[name]	Project Manager	RCSI, Dublin	Children's Health Ireland, Dublin		
[name]	Sponsor Contact	RCSI, Dublin			
TBD	RECOVER Monitor	RSCI, CHI at Crumlin, Dublin	Children's Health Ireland, Dublin		
[name]	Adherence Sub-Study lead, PhD Student	RCSI, Dublin	Children's Health Ireland, Dublin		
[name]	CFRI Representative	CF Registry of Ireland, Dublin	University College Dublin		
[name]	Data Manager	Children's Health Ireland			
[name]	Statistician	Children's Health Ireland	RCSI, Dublin		
[name]	Project manager	RCSI, Dublin	Children's Health Ireland, Dublin		
PPI Representatives	i loject manager		Children's Health Ireland, Dublin		
[name]	CF Ireland Rep	Cystic Fibrosis Ireland			
[name]	Patient Representative				
[name]	Parent Representative				
Clinical site Investiga			1		
[name]	Site PI	Children's Health Ireland at Crumlin	University College Dublin		
[name]	Site PI	Children's Health Ireland at Tallaght	Trinity College Dublin		
[name]	Site PI	Children's Health Ireland at Temple Street	RCSI, Dublin		
[name]	Site PI	University Hospital Limerick	University of Limerick		
[name]	Site PI	St Vincent's University Hospital, Dublin	University College Dublin		

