- 4. To determine the longitudinal effect of ETI on nutrition, gastrointestinal symptoms, gut inflammation and pancreatic function in children and adults with CF over an additional period of 5 years.
- 5. To determine the longitudinal effect of treatment with ETI on CF liver disease in children and adults with CF over an additional period of 5 years.
- 6. To determine the longitudinal effect of treatment with ETI on antibiotic treatment of pulmonary disease in children and adults with CF over an additional period of 5 years.
- 7. To determine the longitudinal changes in mental health outcomes associated with the use of ETI in children and adults with CF over a period of 5 years.

BACKGROUND AND SIGNIFICANCE

Cystic Fibrosis

Cystic fibrosis (CF) is the most common progressive life threatening genetic disease in Caucasians(1). Approximately 80,000 people in the world and 1,200 people in Ireland have CF, almost half of whom are children (CFRI annual report 2016). CF is a multisystem disorder caused by a mutation in a gene that encodes cystic fibrosis transmembrane conductance (CFTR) protein. Lung disease is responsible for the majority of the morbidity and mortality in CF. Predicted survival for individuals with CF currently exceeds forty years, however the current mean age of death is still in the twenties(1). Medications that can modulate the natural history of CF and minimize, or even prevent, the development of life-threatening consequences of CF have been long sought after, particularly if these can be commenced in young children prior to the development of organ damage and irreversible disease.

CF Lung Disease

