Sputum samples will be collected and stored on all participants annually, and these samples will be used for collaborative projects, however detailed analysis of these specimens will not be part of the extension study.

Sputum processing

As part of standard clinical care, sputum or oropharyngeal specimens (OPS) will be collected and processed in clinical laboratories. This data will be stored on local hospital systems and uploaded in the usual way from each center to the relevant national registry, our collaborators in this study. Separate to this, sputum samples for research purposes will be collected at study visits and immediately processed in the laboratory. Measurement of markers of inflammation in sputum is greatly facilitated by having a detailed and reproducible protocol for processing of fresh sputum specimens after collection. We will use such a system to ensure that our samples are collected, handled and processed to the highest level of quality during the study (138). Briefly, according to the TETRIS protocol, sputum will be collected from subjects, either spontaneously or after hypertonic saline induction, and immediately placed on ice for transport to the laboratory. The two-step temperature controlled process will be followed according to the protocol, however, once sputum plugs have been homogenized with cold phosphate buffered saline (PBS), and prior to centrifugation, an aliquot of this homogenized sputum will be mixed with an RNA preservative (RNAlater) and frozen at -80°C for later 16s shotgun sequencing. Sputum supernatant, once processed by TETRIS, will be aliquoted and stored at -80°C.

If a subject is not in a position to produce sputum, the research nurse/coordinator will arrange for sputum induction to be carried out. Sputum induction will be performed by using 7% hypertonic sodium chloride solution will be nebulized for 15 minutes with the subject encouraged to carry out airway clearance maneuvers during and after nebulization. All sputum collected over a 30-minute period will be utilized.

Nasal Lavage

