At the end of the parent study, the liver disease status of participants (CFLD, non-specific [NSCFLD] and No LD) will be updated based on study assessments and review of study worksheets. Proportions of subjects in each group will be compared before and after modulator therapy in addition to determining how many individuals from each given group move to another group on ETI. This will be compared to historic natural history data from the ILSCFLD study for ROI participants.

Classification as part of extension study

Classification will be assigned to each participant as having CFLD, NSCFLD or NoLD annually during the extension study as above.

Specific Aim 6 for Parent Study and Extension Study – Pulmonary Exacerbations and Antibiotic Use

IV Antibiotic Therapy

The number of courses of IV antibiotics (hospitalizations and home IVs) and their indication (elective or unplanned) will be recorded over the duration of the study. This data will be collected in conjunction with clinical staff at local sites. The number (and number of days) of IV antibiotic courses over the length of the study timeframe will be compared with the number of IV antibiotic courses (and days) in the five years prior to commencement of ETI. Some individuals will have started on previous generations of CFTR modulators in the two to three years prior to the initiation of ETI, in which case data will be available for IV antibiotic courses before and on previous CFTR modulator therapy as well as on ETI.

Oral Antibiotic Use

The number of courses, total number of days and type of oral antibiotics will be collected from pharmacy records submitted with parent/guardian consent (and ethical approval) at the end of the study period as part of the adherence arm of RECOVER. The number of courses and number of days of oral antibiotic use will be documented in the eCRF. Given the complexity of the system at UK sites for collection of this information, data on oral antibiotic use from community pharmacies will be collected only from sites in Ireland.

Analysis of Data

Given the depth of information collected through RECOVER we will be in a position to compare antibiotic use to pulmonary outcome measures such as lung function, structure and inflammation, and non-pulmonary indices such as sweat chloride and medication adherence.

Definition of Exacerbation

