We are specifically avoiding defining exacerbations in this study. While a definition of an exacerbation might assist in terms of standardization of between site comparisons, it will introduce some confusion with so many sites involved, is prone to some level of subjectivity and may influence decision making around treatment. In essence comparisons between groups in terms of antibiotic use will be based on internal comparisons between an individual's treatment by the same medical team using similar criteria before and after the introduction of Kaftrio, so will still be valid without specifying criteria. In this case we will be assessing, in a real-world setting, differences in use of antibiotics as opposed to differences in exacerbation frequency. This is

ultimately a more meaningful outcome measure in our view as it is what is of importance to the individual in terms of their treatment.

Risks with Exacerbation Data Collection

We do not foresee any risks in relation to collection of data for IV antibiotic use as this will be readily available and accessible at all sites. Oral antibiotic usage data will be collected through pharmacy records. In previous studies we have used parent report of oral antibiotic courses but found this to be unreliable and subject to considerable bias. The extrapolation of courses of antibiotics from the pharmacy records is likely to overestimate antibiotic use as some courses or parts of courses may be collected but not be taken. This is likely to some degree to even out over time as we are measuring courses per year. We do not foresee difficulties in obtaining pharmacy records. We have used this approach in previous studies and found the uptake to be good. Our study team setup and monitoring plan is likely to ensure that data is collected in a timely and complete way.

Specific Aim 7 for Parent Study – Treatment Adherence

This specific aim will form part of the RECOVER parent study but not the extension study.

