The PROMIS Pediatric Anxiety Scale (Short Form – 8a) and Depressed Mood Scale (Short Form – 8a) are brief self-report measures that can be administered to children from the age of 8 years, providing discreet measures of depressed mood and anxiety for younger children (153). This will represent the first self-report of younger children's emotional experience of CF in a large-scale study (118, 153). In addition to the parent-report PSC Attention subscale, neurocognitive functioning will be measured by the PROMIS Pediatric Cognitive Function Scale (Short Form 7a). This is a brief self-report measure of children's experiences of attention, memory, and comprehension, which is validated for use from the age of 8 years. There is also an adult version (Short Form 8a) which will be used for patients over the age of 18 (153). Body image will be assessed using a three-item questionnaire designed for this study, completed by children from the age of 8 years.

A linear mixed model for each of the mental health outcomes will be used to investigate impacts of patient characteristics over time. Fixed effects in the model will be: age at ETI initiation, genotype, sweat chloride level, nutritional status, caregiver burden scores, number of treatments, year. The model will use random intercept for patient.

The RECOVER distress protocol as shown in Table 10 below will be utilised as needed for participants completing questionnaires.

Table 10: Distress protocol for participant completing interview or questionnaires. (154, 155)

Statistical Analysis

Statistical support and analysis will be provided by CFRI for the parent study and by the Research Data Science team at CHI in conjunction with the Data Science Centre in RCSI for the extension study. Data management and analysis will be carried out using SAS version 9.3 for the parent study and STATA V17.0 for the extension study.

Sample Size and Power for the Parent Study

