Eligibility Assessment	Х	Х															
Sweat Chloride		Х				Х		Х				Х	Х	х	Х	х	Х
LCI	Х	Х				Х		Х		Х		Х	Х	Х	Х	Х	Х
Spirometry-controlled CT (A*)		Х						Х				Х		X1		X1	
Height/Weight/BMI*	Х	Х			Х	Х	Х	Х	Х	Х	Х	Х	Х	Х	Х	Х	Х
FEV1*	Х	Х			х	Х	Х	х	Х	Х	Х	Х	Х	х	х	Х	Х
Airway Sampling (Micro)*	Х	Х			Х	Х	Х	Х	Х	Х	Х	Х	Х	Х	Х	Х	Х
Nasal Lavage (A*)		Х				Х		Х				Х	Х	х	х	Х	Х
FeNO	Х	Х				Х		Х									
Liver Function Testing*		Х			Х	Х	Х	Х				Х	Х	х	Х	Х	Х
Liver Ultrasound		Х						Х				Х	Х	Х	Х	Х	Х
Sputum Collection (A*)		Х				Х		Х		Х		Х	Х	х	Х	Х	Х
Liver Examination		Х						Х				Х					
Stool Collection		Х	Х			Х						Х	Х	х	Х	Х	Х
Blood Collection		Х						Х				Х	Х	Х	Х	Х	Х
Breath Sample Collection		Х			Х	Х	Х	Х									
Abdominal Symptom Score	Х	Х	Х	Х		Х		Х				Х	Х	х	Х	Х	Х
CFQ-R		Х				Х		Х				Х	Х	Х	Х	Х	Х
Pharmacy Records MPR								Х				Х					
Adherence Questionnaire	Х	Х			Х	Х	Х	Х	Х	Х	Х	Х					
MEMs Caps Reading (M)								Х				Х					
Antibiotic Use		Х						Х				Х					
Adverse Event Check			Х	Х	Х	Х	Х	Х	Х	Х	Х	Х	Х	Х	Х	Х	Х
Mental Health Questionnaire													Х	Х	Х	Х	Х

* Collected as normal clinical care,

A - Advanced arm testing in RECOVER parent study

¹ Only for patients who performed spirometry-controlled CT in parent study. Scan at years four and six at sites doing routine clinical CT. Scan at year six for sites not performing biennial CT

M - MEMs study only

Table 14. Schedule of assessments. Each visit has a study window. For the RECOVER parent study the baseline visit (0 month visit) will have an 8 week pre commencement on ETI start window. The 1, 2 and 3 month visits have +/- 2 week window. The 6, 9, 12, 15, 18, 21 and 24 month visits have +/- 1 month window. For the RECOVER extension study each annual visit will have a window of +/- 4 month.

Study Governance and Management Plan

RECOVER

[figure not shown]

Figure 6 RECOVER study management structure.

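### The visit schedule does not support extension Aims 5 and 6 as written: oral antibiotic use has no data source after month 24, and the inputs to the annual liver class change at year 3

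*Protocol*

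**What the plan says.** **Aim 6.** The extension aim is "To determine the longitudinal effect of treatment with ETI on antibiotic treatment of pulmonary disease" over an additional five years. In Table 14 the row "Antibiotic Use" is marked at months 0, 12 and 24 only. The Specific Aim 6 section is headed for both studies. Its IV paragraph says that courses "and their indication (elective or unplanned) will be recorded over the duration of the study". Its oral paragraph takes courses and days from pharmacy records, collected "at the end of the study period as part of the adherence arm of RECOVER", and limits community-pharmacy data to Irish sites. The section on the adherence aim states: "This specific aim will form part of the RECOVER parent study but not the extension study".

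**Aim 5.** The extension paragraph reads: "Classification will be assigned to each participant as having CFLD, NSCFLD or NoLD annually during the extension study as above". The method it refers back to combines examination (hard liver, enlarged spleen), ultrasound and blood tests on a worksheet that two hepatologists review. Both the examination section and the worksheet are labelled for the parent study. Table 14 marks liver examination at months 0, 12 and 24.

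**Aims 3 and 7.** Of the annual sputum samples, the Aim 3 section says: "however detailed analysis of these specimens will not be part of the extension study". The fixed effects of the Aim 7 mixed model include "caregiver burden scores, number of treatments, year".

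**The concern.** An aim is only as good as the data the schedule tells sites to collect. If sites follow Table 14, two things happen at year 3.

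First, antibiotic use drops out of the visit programme, although Aim 6 promises five more years of it.

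Second, the liver class keeps its name but loses one of its three inputs. The protocol's background on CF liver disease makes clinical evidence one route into CFLD, while non-specific ultrasound or biochemical findings alone give the milder NSCFLD class. Removing the examination therefore tends to move people one way, towards the milder class. That is also the direction of the study hypothesis, which expects liver outcomes to improve on ETI. A change in measurement could be read as a treatment benefit.

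**Working it through.** No power or sample-size figure is involved. The check compares each extension aim with the five extension columns (years three to seven) of Table 14.

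| Table 14 row | Parent months marked | Extension visits marked |
|---|---|---|
| Antibiotic use | 0, 12, 24 | 0 of 5 |
| Pharmacy records (MPR) | 12, 24 | 0 of 5 |
| Liver examination | 0, 12, 24 | 0 of 5 |
| Liver function tests | 0, 3, 6, 9, 12, 24 | 5 of 5 |
| Liver ultrasound | 0, 12, 24 | 5 of 5 |
| FeNO | -3, 0, 6, 12 | 0 of 5 |
| Sputum collection | 0, 6, 12, 18, 24 | 5 of 5 |
| Nasal lavage | 0, 6, 12, 24 | 5 of 5 |
| Mental health questionnaire | none | 5 of 5 |
| Caregiver burden | no row | no row |

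**Aim 6, oral use.** The named source is the pharmacy record. It belongs to the adherence arm, that arm is excluded from the extension, and its Table 14 row has no extension marks. The protocol offers no substitute:
- It describes parent report of oral courses as unreliable and biased.
- Pulmonary exacerbations are normally non-reportable as adverse events.
- Registry linkage is not named as a source for this aim.

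**Aim 6, IV use.** The text plans recording throughout, under a heading that covers the extension. Table 14 shows nothing after month 24. This is a contradiction between text and schedule; a plan does exist.

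**Aim 5.** Examination contributes at 3 of 3 parent assessments and 0 of 5 extension assessments. Liver function tests continue. Ultrasound is marked every year, and spleen size is measured on it. The text on ultrasound is not uniform, however. The Aim 5 introduction makes extension scans depend on clinical indication, adding that most sites screen annually. The Ultrasound section says scans will be done for the study where they are not routine, and Table 14 marks all five years. If f is the share of people in the CFLD class who are there on examination findings alone, up to f of that class could be reclassified at year 3 with no change in disease. The protocol gives no value for f, so the range runs from none to all.

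**Aim 3.** FeNO ends at month 12. Statements on the extension specimens conflict:
- The Aim 3 section excludes detailed sputum analysis, and the extension biosample plan stores sputum for future analysis, but the storage section refers to storage and analyses.
- The Nasal Lavage section stops at one year and the extension biosample plan omits lavage, but Table 14 marks it every year and the background says nasal inflammation is tracked throughout.

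**Aim 7.** Caregiver burden is one of seven fixed effects. No instrument for it is named anywhere in the protocol.

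**The case against.** The best counter-argument is that much of this is a table failing to mirror the text. IV courses are to be recorded throughout, the protocol calls those data readily accessible at every site, and the planned comparison already reaches back five years before ETI. IV use can therefore be recovered from records without a visit. That stands, and it limits the IV part to a reconciliation. It does not help oral use. Pharmacy collection at the end of the study period might be read as the end of the extension, but the adherence section and the pharmacy row in Table 14 both rule that out.

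On Aim 5, liver function tests and ultrasound continue, spleen size is still measured, CFLD can also be assigned on histology or radiological portal hypertension, and the worksheet has a field for whether an examination was done. All of this may make the shift small. None of it restores the hard-liver finding, and the protocol does not say how to class a person whose examination is missing.

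A reader might infer that Aims 3, 5, 6 and 7 cannot be answered at all, or that antibiotic and inflammation data are wholly absent for five of seven years. The protocol does not support that. Sputum, nasal lavage and airway cultures are scheduled at all five extension visits, extension Aim 3 states no five-year period, and the mental health outcomes are collected annually. Caregiver burden was never scheduled, so nothing was stopped; it is one covariate without an instrument.

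**Conclusion.** The point holds for Aims 5 and 6. Followed as written, the schedule leaves oral antibiotic use with no data at any of the five extension visits, and it contradicts the text on IV use. It also changes the inputs to the liver class at year 3, in a direction that can look like benefit. The size of that shift cannot be derived from the protocol. The conclusion assumes that sites collect by Table 14 and that the class is meant to be compared across years, as a longitudinal aim implies.

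Aims 3 and 7 contain lesser inconsistencies. Still answerable are Aim 7, the infection part of Aim 3, IV use in Aim 6, and the liver function and ultrasound outcomes in Aim 5. The parent study's primary outcome is not affected.

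**What to change.** In one amendment:

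- **Aim 6.** Add annual IV courses and days to Table 14 for years three to seven. Then either limit extension Aim 6 to IV use or extend the pharmacy extract, with the consent and approval it requires.
- **Aim 5.** For longitudinal comparison, derive the class at every time point, parent study included, from the items collected throughout; or record the two examination items annually. The first needs no new data but gives up the examination finding. The second cannot recover visits already past.
- **Ultrasound.** Reconcile the indication-based wording in the Aim 5 introduction with the Ultrasound section and Table 14. A class built on common items depends on this.
- **Aim 3.** Reconcile the statements on extension sputum and nasal lavage, and word the inflammation part of the aim to match what will be assayed.
- **Aim 7.** Remove caregiver burden from the model, or name its instrument and schedule it.

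The cost is changes to schedule and wording plus a short annual data-entry task. Extending the pharmacy extract would add work at the Irish sites, the only ones that supply community-pharmacy data on oral antibiotics.
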